In 2018 I did a chart review of 180 cases of low back pain in which I tested those who did not have lumbar pain using the SIFFT^x. I treated them with the appropriate exercise depending on the direction of the sacroiliac rotation. From this review, I found 16 cases of pain coming from the lumbar spine (9%). Of the remaining 164 given the appropriate 2 minute exercises, 78% found pain relief of which two thirds left the office entirely pain free. At that time, I also prescribed a pelvic support belt as, generally, a malrotated pelvis is an unstable pelvis^{xi}. As soon as the pelvis becomes malrotated again, the pain recurs. As the corrective exercise and pelvic support belt are two different treatments, the current research project will study them first separately for one month, then on follow-up after they have been used together for one month.

The aim of this study is to determine whether the pain relief and improved back function is temporary or if it can be reproduced and sustained by the patient at home, as needed with these two treatments. In order to test the effectiveness of each treatment alone and when they are combined, two sub-studies will be carried out as follows:

The first study is a superiority trial with a delayed control.

Population: ambulatory people between the ages of 19 and 90 suffering from low back pain, not of lumbar spine or hip origin, for at least three months.

Intervention 1 : teaching participants how to detect pelvic malrotation using the SIFFT then prescribing a two-minute exercise to correct pelvic malrotation, depending on its direction.

Intervention 2: prescribing a pelvic support belt to stabilize the pelvis.

Control: waiting list for one month, using usual treatments such as medications, alcohol and other drugs, chiropractic and other manipulation and physical therapy.

Outcome: a clinically significant change in Brief Pain Inventory (BPI) NRS pain score or in Oswestry disability Index (ODI) for low back pain.

Time: outcomes measured at baseline and after one month of using the assigned treatment at home.

The second study is a one month follow-up of the combined treatments.

Population: all previous study participants

Intervention: teaching all participants how to detect pelvic malrotation using the SIFFT then a two-minute exercise to correct pelvic malrotation depending on its direction followed by prescription of a pelvic support belt.

Control: BPI NRS pain severity score and ODI at one month assessment

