1.2. Hypotheses

The first study aims to find out if the recently developed exercises or the use of a pelvic support belt provide more than short term pain relief in the doctor's office:

Primary Hypotheses for the first study:

1. At 1 month, there will be significantly greater improvement in the ODI for low back pain score: at least 10% greater in those who are in treatment group 1 and are immediately taught how to perform the SIFFT followed by the appropriate exercise when compared to those on the waiting list for one month prior to being treated.
2. At 1 month, there will be significantly greater improvement in the ODI for low back pain score: at least 10% greater in those who are in treatment group 2 and are immediately given the pelvic support belt when compared to those on the waiting list for one month prior to being treated.

Secondary Hypotheses for the first study:

- 1 At 1 month, there will be significantly greater improvement in the BPI NRS pain severity score in those who are in treatment group 1 and are immediately taught how to perform the SIFFT followed by the appropriate exercise when compared to those on the waiting list for one month prior to being treated.
- 2 At 1 month, there will be significantly greater improvement in the BPI NRS pain severity score in those who are in treatment group 2 and are immediately fitted with a pelvic belt when compared to those on the waiting list for one month prior to being treated.

The follow-up study aims to find out if the recently developed exercises together with the use of a pelvic support belt provided more pain relief than each individual treatment:

Primary Hypothesis for the follow-up study:

- 1 At 2 months, there will be significantly greater improvement in the ODI for low back pain score compared to their one-month score in all participants.

Secondary Hypothesis for the follow-up study:

- 1 At 2 months, there will be significantly greater improvement in the BPI NRS pain severity score compared to their one-month score in all participants.

2.0 Recruitment:

Participants making a first appointment at the clinic for back pain will be in contact with my medical office assistant, [name], and invited to participate in this study. If they would like to participate, she will send them the consent form and eligibility questionnaire. If they are eligible, she will schedule them for their first visit.

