3.2.1 Sacroiliac Forward Flexion Test (SIFFT)

Everyone of the “idiopathic” low back pain participants is asked to stand, with their belt undone, leaning on one of the office counters with their legs vertical and their body, flexed at the hips, horizontal (Figure 1). This causes the innominate bones to be tilted forward with the horizontal body and lifted-up by the vertical legs while the weight of the torso brings down the spine and the sacrum. In this position, the PSISs (posterior superior iliac spines) face the examiner and are easier to palpate. The examiners then run their hands down the iliac crests to

Figure

locate the PSISs. Once these are located, they press down below the PSISs with the ulnar side of their thumbs abutting against the PSISs. They then ask the participants whether and on which side they feel pain. The pain may be due to pressure on the overstrained long dorsal sacroiliac ligaments which stabilize this joint. This is called the sacroiliac forward flexion test (SIFFT).

1: sacroiliac forward flexion test (SIFFT)

- Using a surgical marker, the examiner marks the area between his/her thumb and the PSIS on each side and writes the letter B (for before) on the painful side, on both sides if they have pain on both sides. He/she then asks the participant to stand and places a horizontal level on the lowest mark (Figure 2). He/she then measures the distance between the level and the highest mark in centimetres (Figure 3).

Figure 2: using a level on the lowest PSIS

[figure not shown]
[figure not shown]

Figure 3: measuring the distance between levels

The marks indicate the direction and extent of the malrotation:

- if the PSIS on the painful side is higher than that on the asymptomatic side, there is an anterior malrotation of the painful side ileum on the sacrum.
- If it is lower, there is a posterior malrotation of the painful side ileum on the sacrum.

The physician will record the degree of malalignment and its direction. If the participant is part of group 3 they are given a return appointment to be treated with both the exercises and the pelvic support belt one month later.

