3.3 Assessment Visit (One Month after the Treatment Visit)

- Participants will answer the questionnaire about the medications, alcohol and marijuana as well as the other therapies they use for pain relief.
- They will be given the BPI NRS pain severity scales and the ODI questionnaire.
- They will once again be assessed, marked, measured and treated: this time participants in all treatment groups will be instructed on how to do the SIFFT and the corresponding corrective exercises. All of them will also receive the pelvic support belt.
- Those in group 1 will report on their use and effectiveness of the corrective exercises. They will then be fitted with a pelvic support belt.
- Those in group 2 will report on their use and the effectiveness of the pelvic support belt. They will then be taught the SIFFT and how to use the exercise corresponding to the direction of their sacroiliac malrotation.
- Those in group 3 will be instructed on how to do the SIFFT and the corresponding corrective exercises. They will also receive the pelvic support belt.
-

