5.0 Statistics

5.1 Outcome Measures

5.1.1A Primary Outcomes For the First Study

- difference in the change in ODI score in the initial treatment visit questionnaire and at the assessment visit one month later in the control group compared to the change from the treatment visit questionnaire to the 1 month assessment follow-up visit in the immediate SIFFT and exercise treatment group.
- difference in the change in ODI score in the treatment visit questionnaire and at the assessment visit, one month later, in the control group compared to the change from the treatment visit questionnaire to the 1 month assessment follow-up visit in the immediate pelvic support belt treatment group.

5.1.2A Secondary Outcomes For the First Study

- difference in the change in BPI NRS pain severity scores in the treatment visit questionnaire and at the assessment visit, one month later, in the control group compared to the change from the treatment visit questionnaire to the 1 month follow-up assessment visit in the immediate SIFFT and exercise treatment group.
- difference in the change in BPI NRS pain severity scores in the treatment visit questionnaire and at the assessment visit, one month later, in the control group compared to the change from the treatment visit questionnaire to the 1 month follow-up assessment visit in the immediate pelvic support belt treatment group.

5.1.1B Primary Outcome For the Follow-up Study

- difference in the change in ODI score in the assessment visit questionnaire and at the reassessment visit, two months later, for all groups.

5.1.2B Secondary Outcome For the Follow-up Study

- difference in the change in BPI NRS pain severity scores in the assessment visit questionnaire and at the reassessment visit, two months later, for all groups.

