5.2 Statistical Analysis

Data will be analyzed using PASW Statistics 18, Release 18.0.0, IBM. Analysis will be performed by intention-to-treat. Descriptive statistics (mean value \pm standard deviation (SD)) will be calculated for outcome variables at each time point. Baseline between-group data will be analyzed for significant differences by t-tests for nominal variables and Pearson chi square tests for categorical variables. Baseline characteristics will be included in the model as covariates for those variables with a significant between group difference. Analyses of covariates will be applied to compare the groups for magnitude of change in the 0-10 NRS pain score and Oswestry Disability Index between baseline and each follow-up time point (0, 1 and 2 months). A two-tailed P value $<.05$ will be used as the statistical significance level.

- a Pearson's chi-square-test will be done to assess the significance of the difference in Oswestry low back disability score over a 1 month period between

those who are treated with the immediate SIFFT and exercise treatment group, the immediate pelvic support belt group and those who are in the observation group.

- A second Pearson's chi-square will be done to assess the significance of the difference in BPI NRS pain severity score over a 1 month period between those who are treated with the immediate SIFFT and exercise treatment group, the immediate pelvic support belt group and those who are in the observation group.
- A student t-test will be done to assess the significance of the difference in ODI score over a one month period when both treatments are used simultaneously.
- A student t-test will be done to assess the significance of the difference in BPI NRS pain severity score over a one month period when both treatments are used simultaneously.
- The average and standard deviation for all the other data will be calculated and reported on.

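### The follow-up study's before-after t-test has no untreated or single-treatment reference, so it cannot show that the combined treatment works or beats either treatment alone

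*Combined protocol and SAP*

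**What the plan says.** Section 1.1 sets up two sub-studies "In order to test the effectiveness of each treatment alone and when they are combined". Section 1.2 is more specific about the follow-up study: it should find out whether the two together relieve pain better than each one singly.

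The comparator is the participants' own earlier score: "Control: BPI NRS pain severity score and ODI at one month assessment". The primary hypothesis is that at 2 months "there will be significantly greater improvement in the ODI for low back pain score compared to their one-month score in all participants". The primary outcome in 5.1.1B is the "difference in the change in ODI score in the assessment visit questionnaire and at the reassessment visit, two months later, for all groups". Section 5.2 gives the test, "A student t-test will be done to assess the significance of the difference in ODI score over a one month period", covering the month in which both treatments are used. A parallel t-test is planned for BPI pain.

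At the one-month visit (section 3.3), "this time participants in all treatment groups will be instructed on how to do the SIFFT", and all of them also receive the belt. Group 3 reaches this point from the waiting list: at the first visit "they are given a return appointment to be treated with both the exercises and the pelvic support belt one month later".

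**The concern.** A before-after test asks whether the mean change differs from zero. It does not ask whether treatment caused the change. With no concurrent group off treatment, natural course, repeat completion of the questionnaires, changes in other therapies and expectation all enter the estimate. The first study guards against this with a randomised waiting list. The follow-up study has no such guard.

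Pooling adds a second problem. In groups 1 and 2 the month 1 to 2 change follows the addition of a second treatment to the first. In group 3 it follows a move from waiting to both. One mean over all 60 answers neither the effectiveness question in 1.1 nor the comparison with single treatments in 1.2.

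The follow-up primary could therefore be significant, and be read as evidence for the combination, when the combination does nothing.

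**Working it through.** **Inputs from the documents.** 20 per group, 3 × 20 = 60 (section 2.2, described as a pilot size); two-sided 0.05 (section 5.2); both treatments for everyone in month 2 (section 3.3). No power, SD or expected drift is given, so there is no planned power figure to reproduce. Drift, SD and correlation below are assumptions.

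**Step 1. Chance of a significant result with no treatment effect.** For a paired t-test with n = 60, the statistic is noncentral t with 59 df and noncentrality drift × √60 / SD of change; the critical value is 2.00. For drift 3 and SD 12 the noncentrality is 3 × 7.746 / 12 = 1.94, and the probability is 48%.

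| SD of change | drift 1 | drift 2 | drift 3 | drift 4 |
|---|---|---|---|---|
| 8 | 16% | 48% | 82% | 97% |
| 12 | 10% | 25% | 48% | 72% |
| 16 | 8% | 16% | 30% | 48% |
| 18 | 7% | 14% | 25% | 40% |

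With no drift it is 5%.

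**Step 2. Does another planned analysis supply the reference?** Section 5.2 also plans a covariance analysis comparing groups for change to 2 months. By then all groups have had the combination. In 20,000 simulated trials with a true 10-point effect of the combination common to all groups, a between-group comparison of change to 2 months was significant in about 5%. It does not test that effect.

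**Step 3. What group 3 can offer.** With y0, y1, y2 the ODI at months 0, 1 and 2, the treated-month change minus the waiting-month change is

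C = (y2 − y1) − (y1 − y0) = y0 − 2·y1 + y2.

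With a common SD s and a common correlation r, the variance is 6s² − 6rs², so SD(C) = s·√(6(1 − r)). The 95% half-width is 2.093 × SD(C) / √20.

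- s = 12, r = 0.7: SD(C) = 16.1, half-width 7.5 points.
- s = 18, r = 0.5: SD(C) = 31.2, half-width 14.6 points.

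These inputs imply an SD of one-month change, s·√(2(1 − r)), of 9.3 to 18, which is why Step 1 runs up to 18.

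**Step 4. How the contrast behaves with no treatment effect.** With an SD of change of 12:

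- Drift 4 points in each month: C is significant in 5.1% of simulated trials, the before-after test in 72%.
- Drift 6 then 3 points: C wrongly favours treatment in 0.4%; the before-after test is significant in 48%.

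The opposite bias is also possible. If waiting worsens the month-1 score by d, C is biased towards treatment by 2d, because y1 counts twice; the before-after change is biased by d. With d = 3, n = 20, s = 12, r = 0.7 and no drift:

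- C: bias 6, noncentrality 6 × √20 / 16.1 = 1.67, significant in 35%.
- Before-after in the same 20 people: bias 3, noncentrality 3 × √20 / 9.3 = 1.44, significant in 28%.

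**The case against.** The strongest reply is that the plan is open about this. It calls the second part a follow-up, names the participants' own scores as control, and is sized as a pilot; the randomised comparison is the first study. That is fair, and it limits the severity. But the follow-up still has a primary hypothesis of significant improvement, a P < .05 rule and aims worded as effectiveness and superiority.

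The size of the problem is assumed. At 1 point of drift the test is significant in only 7% to 16% of trials over SD 8 to 18. Section 3.5.1 carries the last value forward, so a missed month-2 visit gives zero change; with 15% missing (assumed), 48% falls to about 42%. Both points stand, and neither removes the bias among those who attend.

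Three stronger readings are tempting and are not supported:

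- *Group 3's waiting month is wasted.* It is the control for both primary outcomes of the first study. It is only not compared with group 3's own treated month.
- *The t-test may be unpaired.* Section 5.2 does not say, but the hypothesis compares participants with their own one-month score, so pairing is clear from context. One word settles it.
- *Regression to the mean must inflate the result.* Sections 2.3 and 2.4 set no minimum ODI or pain score, and any regression after presenting for care would be expected mainly in month 0 to 1, before the period tested here.

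Finally, the group 3 contrast does not answer the aim in section 1.2. It compares the combination with waiting, not with either single treatment, and Step 4 shows that it can err in either direction.

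**Conclusion.** The concern holds for what the follow-up study may conclude. A significant month 1 to 2 change cannot show that the combination works or that it beats exercise or belt alone. This follows from the design and needs no numerical assumption: any non-zero drift raises the rejection rate above 5%. How far is not knowable from the documents. The range of about 7% to 97% rests on the assumed drift (1 to 4 points) and SD of change (8 to 18), with 60 complete cases.

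A reader might infer that group 3's own contrast should become the follow-up primary. It should not: it is not randomised, has 20 people, assumes similar drift in both months, and leaves the question of added benefit over a single treatment open. The randomised first-study comparison at one month is not touched by this point.

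**What to change.** In 5.1.1B, 5.1.2B and 5.2:

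1. Report the month 1 to 2 change in ODI and BPI by randomised group and pooled, as a paired mean change with 95% CI. Describe it as uncontrolled. State that its P value will not be used to conclude that the combination works or is better than either treatment alone, and bring the aims in 1.1 and 1.2 into line.
2. Add, as a supportive estimate and not a replacement primary, group 3's change over months 1 to 2 minus its change over months 0 to 1, with a paired 95% CI. State with it that the contrast:
   - addresses the combination versus waiting only;
   - is not randomised and assumes similar drift in both months;
   - is conservative if untreated improvement slows;
   - is biased in favour of treatment if waiting worsens the month-1 score, which counts twice;
   - has n = 20 and an ODI half-width of about 8 to 15 points (assumed ODI SD 12 to 18, correlation 0.5 to 0.7).

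The cost is wording only. Section 4.2.1 already collects both scores at all three visits. The price is a more modest claim from the follow-up study and a wide interval for the group 3 estimate.

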Appendix 1: Brief Pain Inventory Pain Severity Scale

3.	Please rate your pain by circling the one number that best describes your pain at its worst in the last 24 hours.										
	0	1	2	3	4	5	6	7	8	9	10
	No										Pain as bad as
	Pain										you can imagine
4.	Please rate your pain by circling the one number that best describes your pain at its least in the last 24 hours.										
	0	1	2	3	4	5	6	7	8	9	10
	No										Pain as bad as
	Pain										you can imagine
5.	Please rate your pain by circling the one number that best describes your pain on the average .										
	0	1	2	3	4	5	6	7	8	9	10
	No										Pain as bad as
	Pain										you can imagine
6.	Please rate your pain by circling the one number that tells how much pain you have right now .										
	0	1	2	3	4	5	6	7	8	9	10
	No										Pain as bad as
	Pain										you can imagine

Appendix 2: Oswestry Low Back Disability Questionnaire

- **Section 1 – Pain intensity**
- 0 I have no pain at the moment
- 1 The pain is very mild at the moment
- 2 The pain is moderate at the moment
- 3 The pain is fairly severe at the moment
- 4 The pain is very severe at the moment
- 5 The pain is the worst imaginable at the moment

- **Section 2 – Personal care (washing, dressing etc)**
- 0 I can look after myself normally without causing extra pain
- 1 I can look after myself normally but it causes extra pain
- 2 It is painful to look after myself and I am slow and careful
- 3 I need some help but manage most of my personal care
- 4 I need help every day in most aspects of self-care
- 5 I do not get dressed, I wash with difficulty and stay in bed

- **Section 3 – Lifting**
- 0 I can lift heavy weights without extra pain
- 1 I can lift heavy weights but it gives extra pain
- 2 Pain prevents me from lifting heavy weights off the floor, but I can manage if they are conveniently placed eg. on a table
- 3 Pain prevents me from lifting heavy weights, but I can manage light to medium weights if they are conveniently positioned
- 4 I can lift very light weights
- 5 I cannot lift or carry anything at all

- **Section 4 – Walking***
- 0 Pain does not prevent me walking any distance
- 1 Pain prevents me from walking more than 1 km
- 2 Pain prevents me from walking more than 500 m
- 3 Pain prevents me from walking more than 100 m
- 4 I can only walk using a stick or crutches
- 5 I am in bed most of the time

- **Section 5 – Sitting**
- 0 I can sit in any chair as long as I like it
- 1 I can only sit in my favourite chair as long as I like
- 2 Pain prevents me sitting more than one hour
- 3 Pain prevents me from sitting more than 30 minutes
- 4 Pain prevents me from sitting more than 10 minutes
- 5 Pain prevents me from sitting at all

- **Section 6 – Standing**
- 0 I can stand as long as I want without extra pain at
- 1 I can stand as long as I want but it gives me extra pain
- 2 Pain prevents me from standing for more than 1 hour
- 3 Pain prevents me from standing for more than 30 minutes
- 4 Pain prevents me from standing for more than 10 minutes
- 5 Pain prevents me from standing at all

- **Section 7 – Sleeping**
- 0 My sleep is never disturbed by pain
- 1 My sleep is occasionally disturbed by pain
- 2 Because of pain I have less than 6 hours sleep
- 3 Because of pain I have less than 4 hours sleep
- 4 Because of pain I have less than 2 hours sleep
- 5 Pain prevents me from sleeping at all

- **Section 8 – Sex life (if applicable)**
- 0 My sex life is normal and causes no extra pain
- 1 My sex life is normal but causes some extra pain
- 2 My sex life is nearly normal but is very painful
- 3 My sex life is severely restricted by pain
- 4 My sex life is nearly absent because of pain
- 5 Pain prevents any sex life at all

- **Section 9 – Social life**
- 0 My social life is normal and gives me no extra pain
- 1 My social life is normal but increases the degree of pain
- 2 Pain has no significant effect on my social life apart from limiting my more energetic interests eg, sport
- 3 Pain has restricted my social life and I do not go out as often
- 4 Pain has restricted my social life to my home
- 5 I have no social life because of pain

- **Section 10 – Travelling**
- 0 I can travel anywhere without pain
- 1 I can travel anywhere but it gives me extra pain
- 2 Pain is bad but I manage journeys over two hours
- 3 Pain restricts me to journeys of less than one hour
- 4 Pain restricts me to short necessary journeys under 30 minutes
- 5 Pain prevents me from travelling except to receive treatment

